Study Title:	A Phase I, randomised, double-blind, placebo-controlled, single-centre, single-dose escalation and multiple-dose, dose-ranging parallel group study to investigate the safety, tolerability, and pharmacodynamics of subcutaneously administered DEN-181 in adult patients with ACPA+ rheumatoid arthritis on stable treatment with methotrexate (MTX).
Investigational Product:	DEN-181 (liposomal formulation of calcitriol and Pro273Hyp collagen ₂₅₉₋₂₇₃ II peptide – GIAGFKGEQGPKE-Hyp)
Indication:	Rheumatoid Arthritis (RA)
Development Phase:	Phase 1
Rationale:	Current treatments to control pathological immune responses during autoimmunity use broad immunosuppressive drugs associated with undesirable side effects. Alternative strategies to induce antigen-specific immunological tolerance to control both cellular and humoral immune responses are desirable. One such strategy is to use the natural process of antigen presentation by dendritic cells (DCs) to control the balance of pathogenic effector T and B cells versus regulatory T cells (Treg). The investigational product DEN-181 is designed to deliver RA-specific auto-antigenic peptide to lymph node DCs in the presence of the NF-κB inhibitor, calcitriol, with the goal of inducing antigen (Ag)-specific immune regulation.
Investigator(s):	[name] [name]
Primary objectives:	To determine the safety and tolerability of single and multiple doses of DEN-181 in patients with ACPA+ RA.
Secondary objectives:	
 To determine the ability of DEN-181 to modulate the total T-naïve, T-effector and T-regulatory cell populations in peripheral blood; To determine the antigen-specific immune response to DEN-181 including the determination of collagen II peptide specific T-naïve, T-effector and T-regulatory cell populations; To determine preliminary clinical efficacy of DEN-181 in MTX-treated early ACPA+RA patients; To monitor plasma concentrations of calcitriol
Exploratory objectives:	To investigate the effects of administration of DEN-181 on immune responses, disease biomarkers and the microbiome using various exploratory assays in blood, urine and the gastrointestinal tract.
Primary endpoints:	Clinical safety observations including changes in vital signs, adverse events, serious adverse events, laboratory abnormalities and withdrawals from study. Adverse event severity will be graded according to Common Terminology Criteria for Adverse Events (CTCAE, Version 4.03). Any exacerbation of RA will be evaluated by the DAS28CRPv4 (Disease Activity Score 28 including CRP assessment 4 variable calculation) scoring system.
Secondary endpoints:	
 Proportion, total number and phenotype of naïve, effector and regulatory T-cell populations (i.e. total, collagen II peptide-specific, haemagglutinin (HA) peptide-specific) measured by flow cytometry and major histocompatibility complex (MHC) II tetramer analysis pre- and post-administration of DEN-181; Mean changes in DAS28CRPv4 from baseline in treatment and control groups; Determination of the concentration of calcitriol in plasma.

CONFIDENTIAL

Exploratory endpoints:	
 • Various exploratory immune assays. These measures of humoral and T-cell responses, may include, but are not limited to, the following: 
 ○ Proportion, number and phenotype of naïve, effector and regulatory T cell populations of other RA autoantigens (e.g., citrullinated vimentin peptide-specific assessments); ○ Peripheral blood interferon-gamma (IFN-γ) enzyme-linked immunospot (ELISPOT) assays to common infectious antigens (cytomegalovirus, Epstein-Barr virus, influenza virus); ○ Proportions and numbers of myeloid (monocyte and DC), B cell, Natural Killer (NK) cell and T follicular helper (Tfh) cell peripheral blood populations; ○ Antibody titres of RA autoantigens including collagen, modified collagen and ACPA; ○ Ex-vivo re-stimulation assays (e.g., as measured by cytokine secretion and tetramer analysis); ○ T-cell receptor sequencing of specific single cell populations. • Various exploratory biomarker readouts which may include but are not limited to the following: cytokine levels, tryptophan/kynurenine levels (HPLC), metabolomics, measures of the cellular transcriptome and the gastrointestinal microbiome.
Study design:	
Randomised, double-blind, placebo-controlled, single centre, single-dose escalation and multiple dose, dose-ranging parallel group study to be performed in 2 parts.
 
 • Part A: Randomised double blind, placebo-controlled, single centre, single-dose escalation study; • Part B: Randomised double blind, placebo-controlled, single centre, multiple dose, dose-ranging parallel group study at two dose levels.
Number of participants:	
Part A: Total=18 Dose Level 1 (4 active, 2 placebo) Dose Level 2 (4 active, 2 placebo) Dose Level 3 (4 active, 2 placebo)
 
Part B Total=40 Dose Group A (15 active, 5 placebo) Dose Group B (15 active, 5 placebo)

Number of centres:	Single centre
Inclusion criteria:	
 1. Diagnosis of RA made by a rheumatologist; 2. HLA-DRB1*0401+, HLA-DRB1*0101+ or HLA-DRB1*0401+HLA-DRB1*0101+ heterozygotes, homozygotes or compound heterozygotes and ACPA+; 3. Treatment with MTX at the same dose for at least 2 weeks prior to planned start of trial treatment; 4. Any swollen joint count at screening (0-28); 5. Age 18-75 years, inclusive; 6. Male or female. Females of child-bearing potential must agree to use two effective forms of contraception from enrolment to completion of the study; 7. Patients must be informed of the investigational nature of this study and give written informed consent in accordance with the institutional and hospital guidelines; 8. Blood glucose, CBC, haemoglobin, platelets, creatinine, bilirubin, and AST/ALT not greater than 1.5 x out of normal laboratory ranges at entry and clinically insignificant in opinion of investigator; 9. Patients agree to forego vaccinations during the course of the study.

CONFIDENTIAL

Exclusion criteria:	
 1. Malignancy; 2. An active inflammatory disease other than RA; 3. Currently receiving or have received treatment with >10mg prednisone daily within the last 2 weeks prior to screening; 4. Current or recent treatment (< 2 weeks prior) with any disease-modifying anti-rheumatic drugs (DMARDS) other than MTX; 5. Serious infection requiring hospitalisation within last 28 days; 6. Receipt of any live attenuated vaccines within 4 weeks prior to entry; 7. Major surgery within last 28 days; 8. Significant cardiovascular, renal, liver, neurological or skin disease; 9. Positive serology for HIV, or infection with HBV or HCV; 10. Current treatment with cytotoxic or immunomodulatory therapies such as radiotherapy, cyclophosphamide, mycophenolate, tacrolimus, PUVA, acitretin cyclosporine or azathioprine; 11. Any known or suspected allergies to the study drug or its constituents including egg products; 12. Inadequate venous access to allow collection of blood samples; 13. History of drug or alcohol abuse; 14. Participation in any other clinical trial; 15. If, in the opinion of the PI, the subject appears not to be able to perform the needed responsibilities of participation in the clinical study.
Part B Specific Inclusion Criteria	Diagnosis of RA made by a rheumatologist within the previous 2 years.
Investigational Product:	DEN-181 is a suspension of egg phosphatidylcholine (EPC) and egg phosphatidylglycerol (EPG) liposomes (approx. 100 nm diameter, lipid molar ratio 90:10) containing collagen II peptide and calcitriol in 2 mL amber glass vials for single use. Each vial contains 1.0 mL extractable volume of DEN-181 containing 0.6 µg/mL calcitriol and 45µg/mL collagen II peptide.
Comparator:	Placebo is sterile saline for injection (0.9% NaCl).
Duration of treatment per participant:	
Screening: Up to 21 days Study period: 56 days
 
Subjects will receive either: Part A- a single administration of DEN-181 with 56 days (8 weeks) of post treatment follow up or Part B- three administrations of DEN-181 at weekly intervals with 42 days (6 weeks) of post treatment follow up (on study period of up to 11 weeks for each participant from the start of Screening to the end of follow-up)

CONFIDENTIAL


Study procedures:
	
Please refer to Table 1
 
This is a randomised, double blind, placebo-controlled, single centre, single-dose escalation and multiple dose, dose-ranging parallel group study to be performed in 2 parts.
 
Part A: Randomised double blind, placebo-controlled, single centre, single-dose escalation study at three dose levels; Part B: Randomised double blind, placebo-controlled single centre multiple dose, dose- ranging parallel group study at two dose levels.
 
The 2 dose levels to be tested in the 2 groups of Part B will be based upon review of the data in respect of safety and immunomodulatory assessments of the three dose levels tested in Part A by a Safety Monitoring Committee (SMC).
 
Screening Potential participants will be required to provide written informed consent prior to any study-specific screening procedures being performed.
 
Study Period Eligible subjects will return at Baseline (Day 1) to be randomised to receive the first treatment
 
Part A Up to 18 eligible participants will be randomised into Part A of the study. Three dose levels will be assessed in a single dose escalation study design. Participants will be assigned to a dose level. Dose Level 1 (4 active, 2 placebo), Dose Level 2 (4 Active, 2 placebo), Dose Level 3 (4 active, 2 placebo). At each dose level two sentinel subjects (1 active, 1 placebo) will be initially randomised. The remainder of the participants will be dosed no earlier than 7 days after dosing the sentinel group. Safety and tolerability at each dose level will be assessed by a Safety Monitoring Committee 14 days after the dose given to the final cohort participant before proceeding to a progressively higher dose level.
 
Part B Up to 40 eligible participants (30 active, 10 placebo) will be randomised into Part B of the study. The dose levels will be determined based on the results of Part A. Eligible subjects will be administered investigational medicinal product (IMP) on Days 1, 8 and 15 in Part B.
 
Vital signs will be recorded prior to all Investigational Medical Product administrations and at 15 minute intervals for 30 minutes following each dose. Vital signs will include supine blood pressure (systolic blood pressure (SBP) and diastolic blood pressure (DBP), heart rate, respiratory rate, and oral temperature. Subjects will be required to remain in the clinic for at least 4 hours after all Investigational Product administrations. Blood will be drawn for limited PK analysis pre-dose and at 1, 2 and 4 hours post administration of IMP in both parts A and B.
 
Participants will be encouraged to visit the study site on the same day every week (± 2 days) to ensure the lengths of the weeks are similar. Physical examinations, adverse events, vital signs, clinical laboratory parameters (haematology, chemistry, urinalysis) and concurrent medications will be recorded throughout the study. Serum pregnancy testing will be conducted for female participants at Screening and urine pregnancy tests before administration of each dose of IMP. If urine pregnancy testing is positive, a serum pregnancy test will be conducted and the IMP will not be administered until the result is available. If the serum pregnancy test is negative, administration of IMP will continue.

--------------------------	--

CONFIDENTIAL

	
If the result of the serum pregnancy test is positive, the participant will be withdrawn from the study and a Pregnancy Notification Form completed. Blood samples will be collected and shipped to nominated laboratories for preparation of serum, plasma and peripheral blood mononuclear cells (PBMCs) for use in immunological analyses.
 
Subjects will be withdrawn from the study if deemed necessary by the PI if their condition cannot be sufficiently controlled with minor adjustments in treatment. All adjustments in treatment will be recorded.

Contraindications:	Severe local or systemic reactions that preclude further administration.
Safety parameters:	Refer to Table 1
Clinical procedures / assessments:	Refer to Table 1
Specialised analyses:	T-cell responses against RA autoantigens (e.g., MHC II tetramer analyses, tetramer-stimulated analyses for intra-cellular cytokines, ELISpot analyses)
Sample size determination:	No formal sample size calculation is proposed for this clinical trial. This clinical trial is a proof-of-principle study and results from this clinical trial will be utilised for power calculations for subsequent studies.
Statistical analyses:	
Planned analyses: A statistical analysis plan (SAP) will be generated prior to database lock that describes the planned statistical analysis of the study. All data will be provided in data listings sorted by treatment group, time since baseline, and subject number. Categorical data will be summarised by the number and percent of subjects falling in each category. Continuous variables will be summarised by descriptive statistics including mean, standard deviation, median and minimum and maximum. Comparisons will be made between post-treatment and pre-treatment values in the DEN181-treated group and between DEN181-treated and placebo-treated groups. Relationships between DAS28CRPv4 and descriptive data will be determined in univariate and multivariate analyses. Multilinear regression models will assess longitudinal trends.
 
Safety will be assessed by summarising adverse events and clinical laboratory tests. Adverse events will be listed and summarised by system organ class and preferred terms (current version of MedDRA) per treatment group. Vital signs and clinical laboratory tests will be tabulated and summarised per treatment group. Adverse event severity will be graded according to NIH CTCAE Version 4.03.

Committees / guidelines:	DEN-181 Safety Monitoring Committee
Special protocol requirement:	None

CONFIDENTIAL

Table 1-1 Table of Assessments

Assessment	Screening	On-Study Period				Exit Evaluation
	Day -35 to -1	D 1	D8	D15	D29	D57
	Visit 1	Visit 2	Visit 3	Visit 4	Visit 5	Visit 6
Written Informed Consent	X					
Eligibility Assessment/Confirmation	X	X				
Medical History	X					
Physical Examination (symptom directed)	X	X	(X)	(X)	(X)	(X)
Vitals Signs/Body Weight/Height ^{1,2,3,4}	X	X	X	X	X	X
Electrocardiogram	X					
Pregnancy Test ⁵ (Part B only)	X	X	(X)	(X)		X
HIV & Hepatitis Serology	X					
HLA Typing (if required)	X					
anti-CCP2	X				X	X
Rheumatoid Factor (RF)	X					
Issue Injection Site Reaction Diary (Part B only)		X	(X)	(X)		

CONFIDENTIAL

Assessment	Screening	On-Study Period				Exit Evaluation
	-35 to -1	D1	D8	D15	D29	D57
	Visit 1	Visit 2	Visit 3	Visit 4	Visit 5	Visit 6
Review Injection Site Reaction Diary (Part B only)			X	(X)	(X)	
Haematology including ESR	X	X	X	X	X	X
Chemistry including CRP	X	X	X	X	X	X
Urinalysis	X	X	X	X	X	X
DAS28CRPv4 evaluation	X	X	X	X	X	X
PBMC processing and storage		X	X		X	
Tetramer Analysis (collagen II and HA)		X	X		X	
Exploratory immune and biomarker assays		X	X		X	X
Plasma Calcitriol assay ⁶ (Part B only)		X	(X)	(X)		
Oral swab; microbiome analysis		X				X
Dispense IMP (Part B only)		X	(X)	(X)		
Administration of IMP (Part B only)		X	(X)	(X)		
Adverse Event		X	X	X	X	X
Concurrent Medications Assessment	X	X	X	X	X	X

CONFIDENTIAL

DEN-181

Dendright Pty Ltd

¹ Height and weight to be performed at Visit 1 only

² Vital signs include resting BP, heart rate, respiratory rate and oral temperature

³ Safety assessments to be performed prior to IMP

⁴ Vital signs to be performed prior to IMP administration and at 15 minutes and 30 minutes following dosing

⁵ Serum pregnancy testing will be conducted in female participants of childbearing potential at Screening. Urine pregnancy testing will be conducted before each administration of IMP. If urine pregnancy test is positive, a serum pregnancy test will be conducted and the IMP will not be administered until the result of this is received. If the result of the serum pregnancy test is negative, administration of IMP will continue. If the result of a serum pregnancy test is positive, the participant will be withdrawn from the study.

⁶ Blood collected for calcitriol assay pre-dose and at 1, 2 and 4 hours after IMP administration

CONFIDENTIAL

Protocol No. DEN-17-01-RA
Version 3.0

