3.2.4 Pharmacokinetics and Toxicokinetics

Following a single subcutaneous dose of DEN-181 at 100, 300 and 1000 µL in the Sprague Dawley Rat, the maximal plasma concentrations of calcitriol (C_{max}) of 1.94 ± 0.04 ng/mL, 4.50 ± 0.23 ng/mL and 10.54 ± 0.64 ng/mL were reached at 3.3, 4 and 4 hours (T_{max}) after dosing, respectively. Analysis of vehicle-treated controls revealed endogenous calcitriol levels of 211 – 333 pg/mL.

The toxicokinetics of DEN-181 were assessed in Sprague-Dawley rats treated with DEN-181 (at low, intermediate or high dose), once weekly (on Day 1, 8, 15 and 22) over 22 days. Samples for toxicokinetic analysis were collected at Day 1 and Day 22. C_{max} was 1.2 to 1.6 ng/mL for the lowest dose, 2.5 to 2.9 ng/mL for the intermediate dose, and 6 to 9 ng/mL for the highest dose with no significant difference between Day 1 and Day 22, and no gender difference observed. While at Day 1, C_{max} was measured 2 hours after administration, generally T_{max} was slightly later at Day 22 (2 – 6 hours). AUC_t was a slightly lower value for males than for females after low dose delivery (17.80 ng/mL*h to 27.16 ng/mL*h), but there was no difference between Day 1 and Day 22. No difference between genders or Day 1 and Day 22 was observed for AUC_t at the intermediate dose (38.02 to 42.20 ng/mL*h). At high doses, females showed higher AUC_t than males (87.00 to 114.1 ng/mL*h). C_{max} and AUC_t showed a less than proportional increase in function of the administered doses for both days and genders. This may indicate a depot like effect, wherein liposomes are retained at the

site of subcutaneous injection for over 24 hours. However, the ratios of C_{max} and AUC_t on Day 1 and Day 22 indicate that there is no accumulation of the drug after repeated dose.

At the NOAEL, exposures to calcitriol (represented by the mean C_{max} and AUC_t) on Day 22, was approximately 2.5 ng/mL and 38.0 hr*ng/mL, respectively, in males and approximately 2.7 ng/mL and 40.0 hr*ng/mL, respectively in females.

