4.2 Endpoints

4.2.1 Primary endpoints:

- Clinical safety observations including changes in vital signs, adverse events, serious adverse events, laboratory abnormalities and withdrawals from study. Adverse event severity will be graded according to CTCAE, Version 4.03. Any exacerbation of RA will be evaluated by using the DAS28CRPv4 scoring system.

4.2.2 Secondary endpoints:

- Proportion, total number and phenotype of naïve, effector and regulatory T-cells measured by flow cytometry and MHC II tetramer analysis pre- and post-administration of DEN-181;
- Mean changes in DAS28CRPv4 from baseline in treatment and control groups;
- Determination of the concentration of calcitriol in plasma.

4.2.3 Exploratory endpoints:

Various exploratory immune assays. These measures may include, but are not limited to measures of humoral and T-cell responses such as the following:

- Proportion and phenotype of naïve, effector and regulatory T-cells specific to other autoantigens (e.g., responses to other autoantigens including cit-vimentin);
- T-cell responses as determined by interferon-gamma (IFN- γ) enzyme linked immunospot (ELISPOT) assays to common infectious antigens (CMV, EBV, influenza);
- CD4 T-cell responses as measured by intracellular cytokine staining (ICS) (e.g., IL-2 and IFN- γ);
- Antibody titres of RA autoantigens including collagen, modified collagen and ACPA;
- Ex-vivo re-stimulation assays (e.g., as measured by cytokine secretion or tetramer analysis);
- T-cell receptor type as measured by sequence analysis on specific single cell sorted cellular populations.

Biomarker readouts may include, but are not limited to the following:

- cytokine levels;
- tryptophan/kynurenine levels (HPLC);
- metabolomics in urine;
- transcriptome analysis;
- microbiome analysis.

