7.3.2 Visit 2 (Day 1) baseline evaluations, randomisation, and study medication dispensing

At Visit 2 the following tests will be performed and documented on the Case Report Form (CRF) prior to administration of the IMP:

- Review of inclusion/exclusion criteria (see Section 6.2 and 6.3)
- Urine samples for urinalysis and pregnancy testing (see Section 7.4.3 and 7.4.6)
- A complete physical examination (see Section 7.4.1)
- Vital signs (see Section 7.4.1)
- Concurrent medication assessment (see Section 9)
- Adverse event questioning (see Section 10)
- DAS28CRPv4 evaluation (see section 7.4.7)
- Blood samples for:
 - Haematology including ESR (see Section 7.4.3)
 - Clinical chemistry including CRP (see Section 7.4.3)
- Blood samples for immunological assessments including (See sections 7.4.3 and 7.4.4):
 - Tetramer analysis (Collagen II and HA)
 - Exploratory Immune assays
- Blood samples for calcitriol concentration assessment (See Section 7.4.3)
- An oral swab will be (See Section 7.4.8)

Once the above assessments have been performed the patient will be randomised and the IMP will be administered.

- Subjects will be observed and vital signs will be measured at 15 and 30 minutes following the administration of IMP
- Subjects will remain in the clinic for at least four hours post-administration of IMP
- Blood samples for calcitriol concentration assessment will be taken 1, 2 and 4 hours after IMP administration

- The subject will be issued with an Injection Site Reaction Diary and instructed to view their injection site (s) at the same time each day and record their findings every day for 3 days.(See Section 7.4.5)

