8.5.3 Dosage and administration of test drugs

For both Parts A and B, the different dosage volumes of IMP will be administered in the following way:

- Subjects will receive 100µl subcutaneous injections approximately 10 cm above the elbow joint overlying the deltoid muscle of the left upper arm. Where possible the same arm will be injected throughout the course of the study.
- For 300µl subcutaneous injections, 150µl will be delivered 10 cm above the elbow joint overlying the deltoid muscle of each upper arm.
- For 1000µl subcutaneous injections, 250µl will be delivered 10 cm above the elbow joint overlying the deltoid muscle of each upper arm and approximately 5 cm from the groin on each upper thigh.

The injection site will be cleaned prior to administration of the IMP by cleaning with an alcohol swab and air dried.

The participant must remain under supervision at the trial site for at least 4 hours after administration of the IMP. Vital signs including heart rate, supine pulse rate, temperature and supine blood pressure (SBP and DBP) and local reaction at the injection site will be assessed following IMP administration.

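### Dosing-day vital signs, part of the primary endpoint, stop at 30 minutes, although patients stay at least 4 hours and the only exposure data (rat) put the calcitriol peak at 2 to 6 hours

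*Protocol*

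**What the plan says.** The primary endpoint in protocol section 4.2.1 opens with "Clinical safety observations including changes in vital signs, adverse events, serious adverse events". Section 13.4.1 repeats vital signs as a primary safety measure, and section 11 puts them in the minimum data that the Safety Monitoring Committee receives.

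The post-dose times are the same wherever a time is given. The synopsis (Study procedures) has readings "at 15 minute intervals for 30 minutes following each dose". Footnote 4 of Table 1-1 reads "Vital signs to be performed prior to IMP administration and at 15 minutes and 30 minutes following dosing". Section 7.3.2 (Day 1) states "Subjects will be observed and vital signs will be measured at 15 and 30 minutes following the administration of IMP", and sections 7.3.3.1 and 7.3.3.2 say the same for the Part B doses on Days 8 and 15. Section 8.5.3 asks for vital signs after administration but gives no times.

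Patients stay in the clinic for at least four hours after each dose. On Day 1, "Blood samples for calcitriol concentration assessment will be taken 1, 2 and 4 hours after IMP administration", and the same draws follow the Day 8 and Day 15 doses in Part B.

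Section 3.2.4 gives the only time course of exposure, in rats. After single doses, peak calcitriol concentrations "were reached at 3.3, 4 and 4 hours". In the weekly-dose study, the Day 1 peak "was measured 2 hours after administration, generally T_{max} was slightly later at Day 22 (2 – 6 hours").

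**The concern.** A first-in-human trial measures a primary safety variable twice in the first half hour after each dose and then not again that day. On the protocol's own animal data, both readings precede the calcitriol peak. The patient nevertheless remains supervised, and staff see the patient for blood sampling at three later times.

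No other scheduled systemic measurement fills the gap. Footnote 3 of Table 1-1 places safety assessments before dosing, the visit lists put haematology and chemistry among the pre-dose procedures, and the electrocardiogram is scheduled at screening only.

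At stake is what a tabulated absence of change on dosing days would mean. The committee that decides on escalation and selects the Part B doses would see it, and it would say nothing about the hours in which exposure may be highest. The collection times are fixed in the protocol, so no later analysis plan can recover readings that were not taken.

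**Working it through.** No sample size, power or event count is involved. The check sets the reading times against the exposure times and the clinic stay.

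**Inputs**

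| Item | Value | Source in protocol |
|---|---|---|
| Post-dose vital signs | 0.25 h and 0.5 h | Synopsis; Table 1-1 footnote 4; 7.3.2; 7.3.3.1; 7.3.3.2 |
| Rat Tmax, single dose | 3.3, 4 and 4 h | 3.2.4 |
| Rat Tmax, weekly dosing | 2 h (Day 1); 2 to 6 h (Day 22) | 3.2.4 |
| Clinic stay | at least 4 h | Synopsis; 7.3.2 to 7.3.3.2; 8.5.3 |
| Calcitriol draws after dosing | 1, 2 and 4 h | Synopsis; 7.3.2 to 7.3.3.2; 13.6.7 |
| Dosing days | Day 1 (Part A); Days 1, 8 and 15 (Part B) | 5.1; 5.2 |

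**Time from last reading to peak** = Tmax − 0.5 h

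- Earliest quoted Tmax: 2 − 0.5 = 1.5 h
- Latest quoted Tmax: 6 − 0.5 = 5.5 h
- Single-dose values: 3.3 − 0.5 = 2.8 h, and 4 − 0.5 = 3.5 h

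Of the two post-dose readings, none lies between 2 and 6 h.

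**Time on site with no scheduled reading** = stay − 0.5 h = 4 − 0.5 = 3.5 h at least. All three draws fall in this interval.

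**Nominal time to the next scheduled reading** (the pre-dose reading where a dose follows)

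- After the Day 1 dose: Day 8 − Day 1 = 7 days
- After the Day 8 dose (Part B): Day 15 − Day 8 = 7 days
- After the Day 15 dose (Part B): Day 29 − Day 15 = 14 days

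**With readings added at the draws:** the times become 0.25, 0.5, 1, 2 and 4 h. Those at 2 and 4 h lie within the 2 to 6 h range. The 1 h reading still precedes it, and nothing after 4 h is covered.

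**Volume of added readings at full enrolment**

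- Part A: 18 patients × 1 dosing day × 3 = 54
- Part B: 40 patients × 3 dosing days × 3 = 360
- Total: 54 + 360 = 414 sets of vital signs

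**The case against.** The strongest reply is that nothing shows a vital-sign effect would follow plasma calcitriol in time. The rat toxicity study (section 3.2.3) found no product-related clinical, neurological, autonomic or behavioural effects at any dose. The calcitriol signals it did find were raised calcium and phosphorus and tissue mineralisation, and calcium, phosphorus and creatinine are in the chemistry panel at every visit. The highest human dose is put at about 11 times below the human equivalent of the rat no-effect level (section 3.3). Early readings also have a clear purpose, since they suit immediate reactions to a product containing egg phospholipids. All of this stands. It lowers the chance that something is missed, but section 10.8 itself says the adverse event profile in humans cannot be reliably predicted.

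A second reply is that safety cover does not end at 30 minutes. Vital signs are taken again on Days 8, 15, 29 and 57, patients are supervised for at least four hours, extra assessments are allowed when clinically indicated (section 7.3), and adverse events are collected throughout. This also stands. A reader might infer that any finding of no vital-sign effect would rest on the first half hour alone; the documents do not support that. The uncovered part is narrower: changes that are transient, cause no symptoms, and fall after 0.5 hours on a dosing day.

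A third reply is that rats are not patients, and that the 6-hour upper end comes from Day 22, after four weekly doses, whereas Part A gives one dose and Part B three. That is correct. The single-dose and Day 1 rat values alone, 2 to 4 hours, still lie beyond the last reading and inside the supervised stay.

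**Conclusion.** The point holds as a gap in the coverage of a primary endpoint. Dosing-day vital signs end 1.5 to 5.5 hours before the range of peak times in the only exposure data provided, and at least 3.5 supervised hours pass without a scheduled reading. The conclusion rests on one assumption that the protocol cannot confirm: that the human calcitriol peak falls in roughly the same range as in rats. It does not require a vital-sign effect to exist, only that the trial be able to describe one if it does.

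Two stronger readings are tempting and should not be drawn. One is that the protocol contradicts itself: it does not, because every timed statement agrees and section 8.5.3, being untimed, conflicts with none. The other is that the trial fails because vital signs are not paired with calcitriol concentrations: relating the two is not an objective, since section 4.1.2 asks only that plasma concentrations be monitored. This is therefore a low-cost improvement, not a correction of an error.

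**What to change.** Keep the 15- and 30-minute readings. On each dosing day, record vital signs just before the existing 1-, 2- and 4-hour draws, so that the venepuncture does not affect them. Tabulate change from that day's pre-dose value at each time. Amend the synopsis, footnote 4 of Table 1-1 and sections 7.3.2, 7.3.3.1 and 7.3.3.2 together so that they remain consistent.

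The cost is a few minutes of blinded staff time and three extra case report form entries per patient and dosing day. No extra visit or longer stay is needed. The limitation is that a peak between 4 and 6 hours would still be missed.

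If the sponsor prefers the present schedule, it should give its reason for stopping at 30 minutes and state, in the report and in the material for the Safety Monitoring Committee, that dosing-day vital-sign conclusions apply to the first 30 minutes only.
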